9.11 Medical-Surgical Procedures and Follow-up of the Clinical Investigation

After obtaining informed consent, the physician will include in the study those patients who, at the screening visit (Visit 0), meet all selection criteria. During the screening visit, the Investigator will also collect demographic data and the patient's medical history.

Enrolled patients, as would also occur if they chose not to participate in the present Investigation, will undergo the surgical procedure (Visit 1) required for the application of the investigational medical device (Chimaera), which marks the beginning of the treatment period.

Following the surgery, the patient will attend five subsequent visits. The first three visits after the surgical procedure are part of the treatment period and are:

- the visit performed at hospital discharge (Visit 2), which, unless complications occur, will take place within 10 days after the date of surgery. During this visit, the physician will perform routine assessments to confirm that the operation and postoperative course have proceeded appropriately;
- the following two visits (Visits 3 and 4), were conducted at 1 month and 3 months after the date of surgery, respectively. These visits conclude the treatment period which, in the absence of complications, is expected to be within 8–12 weeks from the date of surgery, with the consolidation of the treated proximal femoral fracture. Healing will be assessed by the Investigator through radiographic evaluation, performing a qualitative assessment of bone density at the fracture site and the alignment of the bone fragments. Starting from Visit 4 and at all subsequent visits, the Investigator will also complete the Bowers & Parker functional score (efficacy measure) to assess the patient's functional recovery.

For these patients, device removal is not planned unless required due to serious adverse events necessitating a second surgical procedure to complete the treatment of the fracture (safety measure). Once the treatment period is concluded, the follow-up period begins, during which two visits will be conducted (Visits 5 and 6), respectively at 6 months and 1 year after the date of surgery. During these visits, clinical data will be collected to monitor the progression of fracture consolidation, the patient's functional recovery, and the occurrence of any medium-term adverse events.

[figure not shown]
Clinical data from the study will be recorded in the patient's medical chart and entered a validated electronic data capture system provided by Orthofix Srl.

Patients who, for any reason, decide to withdraw their consent to participate in the study before completing the final follow-up visit will continue to receive the same standard of care they would have received had they completed the study.

Note:

The visits and procedures described above are summarized in the patient treatment schedule and in the table of procedures applicable to each visit below.

9.12 Patient treatment schedule

9.13 Table of procedures applicable to each visit

PERIOD		ENROLMENT	TREATMENT				FOLLOW-UP	
VISIT	Number	Visit 0	Visit 1	Visit 2	Visit 3	Visit 4	Visit 5	Visit 6
	Type	Selection	Surgery	Discharge	1° Follow up	2° Follow up	3° Follow up	4° Follow up
	Window	Day 0 ± 1 week	Day 0	Day 5 ± 5 days	Month 1 ± 1 week	Month 3 ± 1 week	Month 6 ± 1 week	Month 12 ± 1 Month
Informed Consent		x						
Verification of Selection Criteria		x	x	x	x	x	x	x
Demographics		x						
Medical History		x						
Radiographic Examination		x	x			x		
Device Implantation			x					
Parker score						x	x	x
Safety Measures			x	x	x	x	x	x

9.14 Predictable factors that can compromise results

The procedures described in this Protocol are part of the normal clinical practice of the Centers involved. In fact, this clinical investigation is observational so it will not change the clinical protocols currently in use in the Centers involved, nor does it involve additional risks for patients and investigators.

In the present clinical investigation, given the type of patients who will be enrolled, two factors are known that could compromise the outcomes and the interpretation of the results, namely:

- For some very elderly patients who have difficulty moving and with impaired cognitive ability, for example due to senile dementia or advanced neurodegenerative diseases, the assessment of functional recovery may be more difficult.

The Bowers & Parker Functional Score⁷ chosen to assess the patient's functional recovery in terms of pain, walking ability and social independence, as described by the authors, precisely because it could be used in high probability on patients unable to answer reliably, it is composed of questions that can also be answered by the patient's companion (e.g. cohabitant, family member, caregiver, social health worker, etc.), understood as a person who lives in close contact with the patient. The companion can also answer by phone and, given the difficulty of moving this type of patient, this possibility will be very useful to limit the loss of data on the patient's functional recovery in the follow-up period.

- The mortality rate of enrolled patients is about 10% at 10 days after surgery and can reach up to 36% at 1 year. Therefore, a high percentage (25% on average) of non-assessable patients, i.e. discontinued before the end of the treatment period for supposed recovery (scheduled for the check-up visit in the third month after the operation), is expected in the present clinical investigation.

In order to increase the probability of reaching the expected sample size, i.e. 300 evaluable patients, i.e. who will complete at least the scheduled follow-up visit at the third month after the operation (Visit 4), the Sponsor has planned the enrollment of 400 patients and has agreed with the Investigators on a patient replacement procedure described below.

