9.4 Endpoint

In the present Clinical Investigation, the two variables chosen as *the primary and secondary endpoints* to measure the primary and secondary objectives of the Survey also coincide with the measures of response to treatment, in particular:

- Primary endpoint (security measure):

the safety of the *Chimaera* will be measured by the percentage of patients who within a 6-month observation period, due to serious adverse events related to *the Chimaera*, will have to undergo a second operation to continue with the treatment of the proximal femur fracture.

- Secondary endpoint (efficacy measure):

the effectiveness of the treatment carried out with *Chimaera* will be measured through the Bowers & Parker functional score for the evaluation of the patient's functional recovery.

Note:

Bowers & Parker's functional score⁷ It is a validated and unanimously recognized reliable score for the evaluation of patients treated following a hip fracture. This score assesses the patient's functional recovery (in terms of pain, walking ability and social independence) compared to the patient's condition before the fracture. The Bowers & Parker score also has predictive value for assessing the long-term mortality of the treated patient, and for planning short-term rehabilitation activities.

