9.6.2 Exclusion criteria

A patient will be considered not eligible for participation if:

- he/she is undergoing surgery to address the sequelae of a previously treated fracture;
- he/she has been diagnosed with a pathological fracture of oncologic origin (primary tumour or skeletal metastasis);
- he/she has been diagnosed with a fracture in the diaphyseal and/or distal region of the femur;
- he/she has been diagnosed with an open proximal femoral fracture (type II or III according to the Gustilo and Anderson classification);
- he/she has been diagnosed with multiple fractures (including bilateral proximal femoral fractures);
- during the preoperative or intraoperative phase, it is decided to treat the fracture with the long version of the Chimaera nail and/or with non-telescopic (fixed-length) cephalic screws;
- he/she has a medical condition that constitutes a contraindication to treatment with Chimaera according to the manufacturer's instructions for use;
- he/she has a suspected or confirmed hypersensitivity/allergy to any component of the device that comes into contact with the patient;
- he/she presents with any clinical condition that, in the opinion of the Investigator, could interfere with the Clinical Investigation procedures or compromise patient safety;
- he/she is concomitantly treated with a non-permitted device that cannot be removed without compromising patient safety;
- he/she is participating in another clinical study or has participated in another clinical study within 3 months prior to signing the informed consent form.

9.7 *Expected Number of Patients to be Enrolled*

Considering the high proportion (approximately 25%) of anticipated premature withdrawals in this patient population, in order to obtain a sample of 300 patients completing the Investigation, a total of 400 patients are planned to be enrolled across 8 sites. Accordingly, each site is expected to enrol approximately 50 patients over a period of 6–8 months (estimate based on the current frequency of Chimaera use as reported by the sites during the feasibility phase).

9.8 *Enrolment Timepoint*

Each eligible patient able to provide consent personally will be considered enrolled in the Clinical Investigation at the time of signing and dating the informed consent form, in accordance with the procedures for collection described in this Protocol.

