9.10 Duration of the Clinical Investigation

The duration of the Investigation for each patient is 12 months, from the signing of the informed consent form to the last follow-up visit.

Considering that the enrolment period is expected to last 6–8 months, the overall anticipated duration of the active phase of the study is 18–20 months, from the signing of the informed consent form by the first enrolled patient to the last follow-up visit of the last enrolled patient.

It is understood that, following the closure of the active phase of the study, unless otherwise agreed with the Investigators and/or Ethics Committees, the Sponsor reserves a period of 6 months to conduct the end-of-study activities, namely:

- database review;
- opening and resolution of potential data clarification requests (queries) to the Investigators;
- preparation of the statistical report;
- preparation of the clinical report;
- site close-out visits;
- end-of-study notifications to the relevant Ethics Committees and Competent Authority.

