9.16 Patient replacement

Upon notification to the Sponsor, no later than the study recruitment period, non-evaluable patients, at the discretion of the Investigator, may be replaced with a patient who will be assigned a new and unique identification code.

Considering the high percentage of withdrawal usually found with this type of patient, this procedure has the sole purpose of increasing the probability of reaching the expected sample size in terms of evaluable patients. It is understood that the Sponsor will also collect, store and analyze data from prematurely discontinued and replaced patients.

10 Clinical investigation monitoring plan

In order to ensure the proper conduct of the study and the correct recording of study data, at least the following monitoring visits will be planned:

- study start visit;
- two monitoring visits during the active conduct phase of the study;
- Closing visit of the study.

It is understood that, if necessary, for example if numerous deviations from this Protocol occur on a Site,

the Sponsor reserves the right to carry out additional monitoring visits during the live phase of the study.

Prior to each visit, the monitor will contact the Investigator to check availability and schedule the date of the visit, after which they will send a written confirmation specifying the purpose of the visit and any documents to be made available.

On each visit, the monitor must:

- check the updating of the study documentation;
- verify that the Clinical Investigation is conducted and that the data are produced, recorded and communicated in accordance with this Protocol, the Code of Good Clinical Practice – GCP and the applicable legislation;
- verify the correctness of the data entered in the data collection form towards the source data;
- implement any corrective actions.

Note:

The Sponsor intends to monitor the totality of data reported in the informed consent forms, inclusion and exclusion criteria, variables related to study endpoints, and all information regarding serious or non-serious adverse events. If deemed appropriate and necessary, the other data from the study may also be monitored.

11 Clinical Investigation Documentation

During the study initiation visit, the monitor will provide the Investigator responsible for the clinical investigation with a file containing all the paper documentation necessary for the management of the study, namely:

- study protocol with related Synopsis and appendices;

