The following table shows the number of patients and the upper limit of the confidence interval for different possible values of the percentage of the primary *endpoint* (calculations were made using the statistical method of the exact binomial):

Percentage of patients with second intervention	Upper limit of the 95% confidence interval	Number of patients observed
3%	8.518%	100
4%	9.926%	100
5%	9.614%	160
6%	9.703%	250
7%	9.958%	400

Based on the frequencies of serious device-related adverse events and/or device failures received by Orthofix Srl through the passive medical device vigilance system since the device was placed on the market, the expected percentage for the primary *endpoint* is no more than 6%. Therefore, the expected enrollment of 400 patients that will potentially allow us to obtain a sample of 300 evaluable patients is considered adequate for the type and objectives of the present clinical investigation.

The clinical data collected during this Clinical Survey will be analyzed through descriptive statistics:

- the *primary endpoint* will be presented as a percentage value and the corresponding 95% confidence interval;
- the *secondary endpoint* (Bowers & Parker functional score) and other radiographic parameters will be presented via quantitative descriptive statistics (mean, standard deviation, median, minimum, maximum, 95% confidence interval).

During the present Clinical Investigation, if necessary, an interim statistical analysis of the collected data could be carried out, e.g. when all patients have completed the third post-operative check-up (expected within 6 months from the date of operation).

The clinical data obtained from this Clinical Investigation will be used to complete the evaluation of the clinical performance and safety of the *Chimaera* in order to confirm that the device can be considered

effective and safe as assumed under development based on pre-clinical evaluations carried out for obtaining the CE mark.

19 Dissemination of results

The Investigators and the Sponsor undertake to keep the clinical data collected through this Clinical Investigation confidential and confidential until the information is made public in anonymized form by the Sponsor at the end of the Investigation.

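### The 6-month primary safety percentage has no stated denominator, and the 300 evaluable patients behind it are Month-3 completers in 9.14 but 12-month completers in 9.7

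*Combined protocol and SAP*

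**What the plan says.** - **Endpoint (9.4).** The primary measure is the "percentage of patients who within a 6-month observation period, due to serious adverse events related to" the device, need a second operation.
- **Sample (Section 18).** Enrolling 400 to reach "a sample of 300 evaluable patients is considered adequate for the type and objectives of the present clinical investigation". Section 18 does not define *evaluable*.
- **Month-3 definition (9.14).** The target is "300 evaluable patients, i.e. who will complete at least the scheduled follow-up visit at the third month after the operation (Visit 4". The expected loss is "a high percentage (25% on average) of non-assessable patients, i.e. discontinued before the end of the treatment period". Section 9.15 uses the same Month-3 cut-off for patients who are not assessable.
- **12-month description (9.7, 9.10).** Section 9.7 plans 400 patients, at about 25% premature withdrawal, "in order to obtain a sample of 300 patients completing the Investigation". Section 9.10 adds: "The duration of the Investigation for each patient is 12 months".
- **Analysis (Section 18).** The primary endpoint "will be presented as a percentage value and the corresponding 95% confidence interval". No denominator is named.
- **Discontinued patients (9.15, 9.16).** Causes of discontinuation include death, loss to follow-up and a serious adverse event that stops treatment from continuing. Under 9.16, "non-evaluable patients, at the discretion of the Investigator, may be replaced with a patient". That section also says that data from discontinued and replaced patients are analysed, but not whether they enter the primary percentage.

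**The concern.** The endpoint looks at 6 months, while the set that the plan counts is fixed at 3 months in one place and at 12 months in another. Month-3 completers need not be followed to Month 6, and they leave out everyone who died or left early. Twelve-month completers are followed long enough, but they leave out patients who had an event, or reached Month 6, and then died or left.

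Leaving can also be related to the outcome. Under 9.15, a patient discontinued before Month 3 because of a serious adverse event that stops treatment is not assessable and may be replaced. Serious device-related events that lead to reoperation are the numerator of the primary percentage. If the evaluable set is the denominator, such events can drop out of the main safety result. Early deaths without reoperation drop out too, which pushes the other way. With 1-year mortality of up to 36% quoted in 9.14, the number of patients affected will not be small.

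**Working it through.** **1. The plan's own figures.** Inflation for 25% loss: 300 / (1 − 0.25) = 400, as stated. The table in Section 18 uses the exact binomial; the two-sided 95% upper limit for x events in n patients is the 0.975 quantile of Beta(x + 1, n − x). All five rows reproduce: 3/100 = 8.518%, 4/100 = 9.926%, 8/160 = 9.614%, 15/250 = 9.703%, 28/400 = 9.958%.

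**2. Is the sample size at fault?** At the expected 6% the table needs 250 patients. 18/300 = 6.0% has an upper limit of 9.32%, and 24/400 = 6.0% has 8.80%. Both are below the 10% aimed at.

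**3. Effect of a completer denominator.** Take the expected 6% in 400 implanted patients: 24 events, 24/400 = 6.0% (exact 95% CI 3.88–8.80%). Let 100 of the 400 be non-completers (the plan's 25%), with x of the 24 events among them. How the events split is an assumption; the documents give no figure.

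Completer percentage = (24 − x) / 300, so each event among the 100 moves it by 1/300 = 0.33 points.

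| Events among the 100 (x) | Completer result | Exact 95% CI |
|---|---|---|
| 3 | 21/300 = 7.0% | 4.39–10.50% |
| 6 | 18/300 = 6.0% | 3.59–9.32% |
| 9 | 15/300 = 5.0% | 2.83–8.11% |

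The result equals 6.0% only at x = 6, when non-completers have the same event rate as completers. With fewer events among them it is too high, and with more it is too low.

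**4. Error of the all-implanted percentage.** This is not free of error either. If a fraction L is lost alive with half of the 6-month risk still ahead (an assumption), a true 6.0% reads 6.0% × (1 − 0.5 × L):

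- L = 5%: 5.85%
- L = 15%: 5.55%
- L = 25%: 5.25%

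The last line treats the plan's whole 25% loss as patients lost alive. If losses are mostly deaths the error is small, because a patient who died without reoperation had no event and can have none later. The error runs in one direction only, downwards, and can be judged once the number lost alive is reported.

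**The case against.** The strongest reply is that *evaluable* is defined once, in 9.14, that 9.15 agrees with it, and that 9.7 never uses the word. The 12 months comes from reading 9.7 with 9.10. On this view *evaluable* is only a recruitment target, the endpoint is a percentage of patients without restriction, and 9.16 promises that discontinued and replaced patients are analysed. Much of this stands. A completer denominator is not a stated rule, and the mismatch in 9.7 taken alone is a matter of wording. But the reply does not supply the missing statement. Section 9.16 does not say where those patients are analysed, Section 9.5 governs only which events count, and no section says how death or loss before 6 months is handled.

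*All enrolled* is not an obvious default either. Enrolment is at consent (9.8), while an intraoperative change to the long nail or fixed-length screws is an exclusion (9.6.2). The enrolled and implanted sets can therefore differ.

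Three stronger readings are tempting but not supported:

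- A reader might infer that the plan will drop early reoperations from its primary result. The text permits this reading but does not state it.
- A reader might infer that an endpoint reoperation is itself an exclusion criterion, because criteria are re-verified at every visit and 9.6.2 excludes surgery for sequelae of a treated fracture. That criterion is most naturally about the operation at entry; 9.4 describes the second operation as continuing the fracture treatment, and 9.11 calls it the safety measure.
- A reader might infer that the study is too small or that a pass mark is at risk. Step 2 above shows that the size is adequate at 6%, and Section 18 states that there is no hypothesis, no direct comparison and no threshold.

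**Conclusion.** The gap is real and should be fixed before analysis. The one definition of *evaluable* does not match the 6-month endpoint, 9.7 describes the same 300 differently, the same 25% loss is tied to two time points, and neither the denominator nor the handling of death and loss is stated.

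The size depends on a split that is unknown. With 24 events in 400 and 100 non-completers, moderate assumed splits move the reported 6.0% to between 5.0% and 7.0%, with upper limits of 8.1% to 10.5%. The 10% figure is a sizing aim, so crossing it triggers nothing, but the reported safety rate changes. Confidence is high that the rule is missing. The direction and size of any bias cannot be known from the documents.

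**What to change.** - In 9.14, 9.16 and 18, define the primary analysis set as all enrolled patients implanted with the short nail and telescopic screw(s), including discontinued and replaced patients. Count every qualifying device-related reoperation within 6 months under the attribution rules of 9.5, unchanged.
- Keep the planned percentage and give its exact 95% CI. Beside it, report how many patients died and how many were lost alive before 6 months.
- Add, as a supporting estimate, the 6-month cumulative incidence of device-related reoperation, with death as a competing event and loss censored at last contact.
- Show the Month-3-completer percentage only as a secondary display.
- State that discontinuation or replacement after an endpoint reoperation does not remove the patient from the primary set. Replacement can stay as additional enrolment.
- Use one definition of the 300, and one time point for the 25% loss, in 9.7 and 9.14.

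The cost is a wording amendment and one standard extra estimate, with no additional patients or visits. Under Section 15, an amendment that the sponsor classes as substantial suspends the investigation until the ethics committees give a new opinion, so the classification should be settled first.
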